The proposed project, Living In Fitness Together (LIFT) tests the feasibility and preliminary efficacy of a group-based PT fall prevention program using a within-group peer coaching intervention to improve outcomes for older adults at risk for falls by promoting sustained patient engagement in exercise and physical activity. The program will consist of group-based physical therapy for balance, strength, flexibility, and mobility training combined with a behavioral theory-based goal-achievement and peer-coaching training intervention targeting self-efficacy for the patients/group participants. It consists of 8 group sessions over 6 weeks plus one group booster session delivered by a physical therapist (PT) and trained staff. The program is designed to: 1) deliver progressive, tailored, and challenging exercise intervention for older adults at risk for falls; 2) empower older adults to achieve the required milestones for exercise and physical activity through training in theory-based behavior change, self-management, peer support and peer-coaching applied among the group participants; 3) incorporate evidence-based home safety intervention with necessary support for implementation of modification recommendations. By focusing on peers empowering each other within PT intervention as the center of exercise-based fall prevention for long-term patient engagement, this project will provide an innovative model for successful fall prevention.

Our Specific Aims are to:

1. Assess the feasibility of implementing the peer-coaching program in the physical therapy practice context by measuring enrollment, attendance, and completion of the program.
2. Evaluate whether the LIFT Fall Prevention program creates long-term behavior change as measured by exercise adherence at 6 months.
3. Evaluate safety and preliminary efficacy of the LIFT Fall Prevention program among 48 patients within an outpatient physical therapy practice. Safety will be assessed using self-reported falls, injuries, and adverse events. To support trial design for a future comparative

trial, we will measure indicators of initial efficacy including lower extremity strength and function, balance, balance confidence, concern about falls, mobility, physical activity, self-efficacy for exercise, and exercise adherence.

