## Control Program

The control group will continue with "usual care" one-on-one physical therapy. In addition, they will attend a control group class that provides social interaction and interesting health information. They will be asked to track when and how much they do their PT home exercise program, walking, and any falls or adverse events or problems. Below is a description of the control group class.

**"Healthy YOUiversity"** is a program developed by Boston University and Mt Ascutney Hospital and Health Center (MAHHC) for the Living In Fitness Together Research Study to provide group education about activities and behaviors that promote healthy living. This 6-session program includes the following topics:

**Home Safety:** Content will be provided in the participant binder to address the range of ways to enhance safety inside and outside of the home. This content will be reviewed in the orientation session so that questions can be answered and participants can expect the OT's call. A Home Safety Assessment by an Occupational therapist will be offered, as described above in the Home Safety Assessment section.

**Session 1. New Stress Paradigm.** This session will discuss stress within the context of the Energy In - Energy Out paradigm. Participants will learn examples of healthy activities and choices across a range of topics including nutrition, sleep, positive thinking, social support, meaningful activities, and exercise. Activities and choices that may deplete energy and overall health will be discussed. Tools such as visual imagery, mindfulness, breathing exercises, and simple techniques to enhance healthy sleeping patterns will be presented. Handouts will be provided in the participant binder.

**Session 2. Nutrition.** This session will teach the heart healthy diet as outlined by The American Heart Association, National Institutes of Health and the American Medical Association. Handouts from government websites will be provided in the participant binder.

**Session 3. Leisure Education for Quality of Life.** This session will explore the PLESS approach to including a variety of healthy leisure activities.

- **P:** Physical
- **I:** Intellectual
- **E:** Emotional/Relaxing
- **S:** Social
- **S:** Spiritual/Meaningful.

**Session 4. Social Capital** This session will define social capital and how it aids a healthy lifestyle. Examples will be discussed including sharing information and resources, providing assistance, and building trust.

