#### **Control Group**

Data will not be entered into eChart for Control Group. Data collection will be filed in a secure place and sent to BU for analysis. Patients will be registered under Recurring encounter for Therapies if they have not started outpatient PT or continue with primary outpatient PT. PT documentation will be performed by the PT as per the outpatient protocol in eChart.

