### **Therapeutic Recreation Services (both groups)**

INTERVENTION GROUP: The therapeutic recreation therapist will document using Recreation Therapy Progress Note. As per usual care, there will be no charges.

CONTROL GROUP – The therapeutic recreation therapist will track attendance and there will not be any additional documentation.

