## **Training**

### **MAHHC Outpatient Physical Therapists**

LIFT investigators will provide information to the Mt Ascutney physical therapists who will be identifying eligible patients during a one-hour session. Information about the study and the eligibility criteria will be provided. The physical therapists will be trained in how to use the eligibility form, and where to submit it (Eligibility Form: Appendix G; Training Form for Outpatient Therapists: Appendix H). Printed copies of the Participant Study Summary will be provided.

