### **Adverse Event Recording from the Baseline Data Collection through Week 6 (in-person classes)**

Because this study includes older adults at increased risk for falls, we expect adverse events in this study to include falls. In addition, we expect adverse events from exercise in both groups to include: fatigue, muscle soreness or other discomfort or a fall or injury during tests and exercise. As per Lamb 2005, falls will be described as "unexpected events in which the participants come to rest on the ground, floor, or lower level." Participants will be provided with the definition of falls used in this study in the Baseline Data Collection & Orientation session (prior to starting the program). They will be provided with their binders, and we will instruct them in the use of the Action plan to record daily any falls or adverse events, symptoms and questions, as they occur. At each session, the instructor will collect the forms, make copies for study documentation, and return them to the participants.

If participants report fall(s) and/or adverse effects/events through the Action Plan (intervention) or Activity Tracker (control), or verbally, in-person or by telephone, the instructor will provide appropriate clinical assessment and recommendations and modifications if safe to continue participating in the program and document in the clinical flow chart. In addition, the instructor will fill out the Adverse Event Form (Appendix P) and provide the form to the research assistant, who will document the event in a master log of all adverse events.

If a participant falls or experiences an adverse event while attending the class session, the instructor will provide appropriate clinical assessment and recommendations and modifications if safe to continue participating in the program and document in the clinical flow chart. If injury occurred and the participant was unable to participate in the class, the instructor will complete and submit an RL Solutions event as per Mt Ascutney procedures. The instructor will determine

whether the participant needs to seek medical attention at MAHHC and assist the participant to the clinic or emergency department. In addition, the instructor will fill out the Adverse Event Form (appendix P) and provide the form to the research assistant for documentation in the master log.

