## **Statistical Analysis Plan**

### **From grant submission 7-27-2015**

Enrollment and safety data will be collected in the study database by the clinical co-investigators. Safety analyses will be conducted based on similarly basic data collection and tracking and will include summary falls, adverse events and protocol deviations, and summary statistics (n,%) calculated. This feasibility study will not be powered to detect differences in outcomes between the 2 groups. We will carefully examine baseline rates of falls and other variables to enable rigorous sample size calculations for a formal clinical trial. However, preliminary analyses of changes in the intervention and control groups will be assessed to inform study planning. We will calculate the means and standard deviations at pretest (baseline) and corresponding values at post-tests (6-week/program completion, 3-month post program, 6-month post program). The corresponding confidence intervals will be calculated to fully describe the plausible true population values. We will explore differences between the intervention and control group in baseline characteristics, and relationships between these variables and outcome variables of interest. Differences between the groups will inform planning for randomization and baseline values may be used to adjust for differences in our preliminary analyses of differences between groups. At each post-test time point, we will apply analysis of covariance (ANCOVA) to examine the relationship between the post-test score and treatment controlling for the pretest score and demographic variables.

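### Up to week 6, adverse events during supervised exercise have two routes into the log in LIFT but only self-report in control, so the safety summary may under-count control events relative to LIFT

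*Combined protocol and SAP*

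**What the plan says.** - **Expected events.** The section on adverse event recording from baseline through week 6 expects exercise-related events in both arms: "we expect adverse events from exercise in both groups to include: fatigue, muscle soreness or other discomfort or a fall or injury during tests and" (sentence cut short here).
- **Self-report, both arms.** Participants log events daily (Action Plan in LIFT, Activity Tracker in control) or tell staff in person or by telephone. The class instructor then completes the Adverse Event Form and the research assistant enters the event in the master log.
- **Witnessed events.** The same section adds: "If a participant falls or experiences an adverse event while attending the class session, the instructor will provide appropriate clinical assessment". The instructor completes the same form. The rule is tied to the class.
- **LIFT supervision.** The Introduction has a PT and trained staff deliver the exercise class. Under Documentation of PT and OT Services, Intervention Group, anyone already in outpatient PT is discharged from it.
- **Control supervision.** The Control Program section keeps controls in usual-care "one-on-one physical therapy. In addition, they will attend a control group class that provides social interaction and interesting health information". That class is six health-education sessions. For the PT visits, "PT documentation will be performed by the PT as per the outpatient protocol in eChart".
- **Training.** For the outpatient PTs: "Information about the study and the eligibility criteria will be provided", plus how to use and submit the eligibility form. Adverse event reporting is listed in the training of LIFT research staff.
- **After week 6.** A blinded assessor telephones participants every 2 weeks with a standard script, and other study staff report events they learn of.
- **Use of the data.** Aim 3 is to evaluate safety and "preliminary efficacy of the LIFT Fall Prevention program among 48 patients within an outpatient physical therapy practice", with participants' own reports named as the safety measure. Under the SAP, the safety analyses "will include summary falls, adverse events and protocol deviations, and summary statistics (n,%) calculated".

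**The concern.** The plan expects exercise to cause events in both arms, but its observer is placed where only one arm exercises. In LIFT the person completing the form is watching the exercise. In control the class instructor is teaching a health topic, and the clinician watching the exercise has no stated part in adverse-event reporting.

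The SAP summarises events as n and %, with no stated split by how an event became known. If participants do not report everything, equal true risk would appear as more exercise-related events in LIFT. Aim 3 would carry that into the safety description of LIFT and the planning of the formal trial. The Principal Investigator's conclusion on the pattern of events at continuing review would probably draw on the same log.

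**Working it through.** The plan states no adverse-event rate, capture rate, margin or test for safety, so there is no figure to reproduce. The check traces the routes and then illustrates their effect.

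**Routes to the master log, baseline to week 6**

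| Where the event happens | LIFT | Control |
|---|---|---|
| Supervised exercise | Instructor witnesses; participant reports | Participant reports |
| Study class | Same sessions as above | Instructor witnesses (education, not exercise); participant reports |
| Home or elsewhere | Participant reports | Participant reports |

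Only the first row is unequal for exercise events. The program content summary gives LIFT 4 × 45 + 4 × 30 = 300 minutes of exercise in classes 1 to 8, all under the witnessed-event rule. No control exercise falls under that rule. The number of control PT visits is not stated, so this compares coverage by a rule, not exposure.

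**Effect on supervised-exercise events.** Let s be the share of these events that participants report and o the share that an observer records, independently. Neither is in the documents. LIFT captures 1 − (1 − s)(1 − o); control captures s. At equal true risk the apparent ratio is [1 − (1 − s)(1 − o)] / s.

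| s | o = 0.5 | o = 0.9 |
|---|---|---|
| 0.5 | 0.750/0.500 = 1.50 | 0.950/0.500 = 1.90 |
| 0.7 | 0.850/0.700 = 1.21 | 0.970/0.700 = 1.39 |
| 0.9 | 0.950/0.900 = 1.06 | 0.990/0.900 = 1.10 |
| 1.0 | 1.00 | 1.00 |

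In counts: 48 participants suggest 48/2 = 24 per arm (inferred, not stated). With an assumed true risk of 20%, 24 × 0.20 = 4.8 events are expected per arm. At s = 0.7 and o = 0.9, LIFT records 4.8 × 0.97 = 4.7 and control 4.8 × 0.70 = 3.4, a gap of about one event. If control PT visits had the same o, the ratio would be 1.00 for every s.

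**Dilution by other events.** Let f be the share of all events that arise in supervised exercise, taken as equal in both arms, with the rest captured at s in both. LIFT captures s + f·o(1 − s) and control s, so the overall ratio is 1 + f·o(1 − s)/s. The documents do not give f. As a rough stand-in, use exercise time with the weekly goal of at least 2 hours (a LIFT 12-week goal, here assumed for both arms and all weeks), and ignore the booster session:

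- Weeks 0 to 6: f = 300/(6 × 120) = 300/720 = 0.417. At s = 0.7 and o = 0.9 the ratio is 1 + 0.417 × 0.9 × 0.3/0.7 = 1.16; at s = 0.5 and o = 0.9 it is 1.38.
- Six months: f = 300/(26 × 120) = 300/3,120 = 0.096. The same two cases give 1.04 and 1.09.

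Falls and symptoms unrelated to exercise lower f further.

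**The case against.** The strongest reply is that self-report is the declared safety measure, both in Aim 3 and in the safety-monitoring paragraph after Figure 2, and that it is collected in both arms. Controls are taught at orientation to record falls and adverse events, the instructor copies their sheets at each session, and any log entry or spoken report leads to the same form. The safety-monitoring paragraph also mentions bi-weekly calls without limiting them to one arm or period. This stands: control events have a route, and it is the treating PTs who lack one. It does not remove the difference, because every one of these routes is self-report and LIFT has self-report as well.

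It is also fair that the safety analysis is descriptive, that the study is not powered for group differences, and that the outpatient therapists' training form and the outpatient protocol are not in the text reviewed. The plan is silent on outpatient PT reporting; it does not forbid it.

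A reader might infer more in three places:

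- **That control events are certainly under-counted and LIFT will look less safe.** The documents give no reporting rate. If self-report is complete, the ratio is 1.00.
- **That the control class may record no adverse events.** Therapeutic Recreation Services says of the control group: "The therapeutic recreation therapist will track attendance and there will not be any additional documentation". That sentence sits among rules on chart notes and charges. The Adverse Event Form is a study form required of the instructor elsewhere, so the sentence needs clarifying but does not cancel the form.
- **That the imbalance runs through all six months.** From week 6 the blinded scripted calls are the same in both arms.

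**Conclusion.** The difference in routes is in the text and needs no assumption: up to week 6, events in supervised exercise have an observer with a reporting duty in LIFT and none in control. Any bias would probably run against LIFT. Its size is unknown. Under the assumed capture rates the apparent ratio is 1.00 to 1.90 for supervised-exercise events, and about 1.04 to 1.16 for all events in the middle case (s = 0.7, o = 0.9), depending on the window. These are illustrations that rest on assumed s, o and f, on independence of the two routes, and on equal true risk.

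Soreness and fatigue seem likelier to go unreported than falls or injuries. With about 24 per arm, a gap of one or two events would be hard to tell from chance, but it could still colour a descriptive safety statement. The point is moderate, cheap to correct, and limited mainly to weeks 0 to 6.

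**What to change.** 1. **Statistical Analysis Plan.** Tabulate falls and adverse events by arm and by source (clinician-witnessed or participant-reported). Base the between-arm safety description on the participant-reported events, which are the declared measure and are collected in both arms. Record every source that reported an event, not only the first. A LIFT participant may not log what the instructor has already noted, so both tables should be shown.
2. **Adverse event recording, baseline through week 6.** Extend the witnessed-event rule to outpatient PT sessions of control participants through week 6, with the treating PT sending the Adverse Event Form to the research assistant. Add this to the existing one-hour session for outpatient PTs.
3. **Therapeutic Recreation Services.** State that the limit on documentation does not cover the study's Adverse Event Form.

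A review of control PT charts to 6 months should not be added on its own. LIFT participants have been discharged from outpatient PT, so events at home that a control participant mentions to the therapist would gain a route that LIFT lacks, and the bias could reverse. If records are reviewed, the same review and time window should apply to both arms.

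The cost is a few minutes of training, an occasional form and an extra column in the safety table. The control event count may rise slightly. Treatment, randomization and outcomes are unchanged.

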### **Adverse Event Recording from Week 6 through Study Completion (6 months)**

To identify adverse events after the regular class sessions have been completed, participants will record the events in their tracking forms, and a blinded assessor (separate from the outcomes assessor, study management and intervention teams) will contact the participants every 2 weeks by telephone to inquire about any events that have occurred. A standard script will be followed during these sessions to obtain consistent information and to maintain blinding (appendix P). The blinded assessor will fill out the Adverse Event Form for any event reported during a call and provide it to the research assistant for documentation and tracking. If the adverse event meets the definition of Unanticipated Problem, the blinded assessor will also notify the principal investigator immediately (same day). The principal investigator will report the Unanticipated Problem according to the BU IRB guidelines stated above. In addition, other study staff will report adverse events if they become aware of them during the post-group class time period (Week 6 – 6 Months) by filling out the Adverse Event Form, providing it to the research assistant, and notifying the principal investigator immediately if the event is an Unanticipated Problem.

### **Preliminary Efficacy Data**

#### **Baseline Data Collection (See Appendix R)**

Both Groups	
Performance-based Measures	Self-report
4-stage Balance	demographics
TUG	LLFDI community mobility short form
30-second Chair Stand	FES-I
DGI	ABC-6
	Barriers Self-Efficacy
	Technology Use Questionnaire
	Get up from floor
	New/change in health status
	Recent fall(s) and mobility questions
	Home Assessment Questions

## **Baseline Data Collection and Orientation**

### **LIFT Intervention group**

Within 2 weeks of the start of the program, the participants will be invited to come to a baseline Data Collection and Program Orientation session. Blinded research staff will provide questionnaires, conduct the physical tests, and complete the Baseline Data Collection Form. The Intervention and Control groups will be invited to separate Data Collection times or rooms in groups of 4. For example, 4 of the Intervention participants will be scheduled for 10:00am on Thursday. They will be shown into one room. The blinded research staff ([name]) will be informed of the room and time, but not the assignment of the group. She will inform the participants that she must not know their assignment. She will instruct the participants to complete the questionnaires, and offer to clarify as needed. While participants are completing the questionnaires, she will conduct the TUG, 30 second chair stand, 4-stage balance test and Dynamic Gait Index (10 minutes) individually. When participants have completed the questionnaires and physical tests, The Data Collector ([name]) will release them to unblinded study staff ([name]), who will bring the participants to the appropriate location for their separate orientation sessions. She will also deliver the physical test results to the Intervention group instructor ([name]) to inform the Orientation session. The orientation will consist of an explanation of the overall structure of the class, provision of the Participant Binder and the activity monitors, and ascertaining the starting weight for strength training. Instruction will be provided on use of the monitors. Participants will be asked to wear the monitors daily and to record their steps in their Action Plan (Appendix B) until the first program session to establish their baseline walking activity. The Action Plan will also be used to track daily symptoms and falls on a daily basis.

